8.7. Outpatient (ambulatory) visit (Day 5) and Follow-up visit (Day 7)

Subjects will return to the clinic for an outpatient visit and the Follow-up Visit, as scheduled in the Schedule of assessments (Section 5). The following assessments will be done.

- Scheduled AE monitoring
- 12-lead ECG
- Vital signs (BP and HR)
- Clinical safety laboratory evaluations (haematology, coagulation, biochemistry, and urinalysis)
- Blood sampling to assay emodepside in plasma
- Physical examination (brief or full) and short neurological examination

A full neurological examination may be conducted, if clinically indicated or to investigate treatment-emergent adverse events.

8.8. Sampling time points and additional tests

With the Sponsor's approval, additional time points may be introduced, and changes to time points may be made, if there is reason to believe that the change might improve the quality of the data (for example, if it is believed that an important effect of emodepside is occurring at a time when no measurements are scheduled), or if extra procedures are needed in the interest of subject safety. However, the total volume of blood taken in the trial will not exceed the value given in Section 8.10 unless in the opinion of the Investigator, it's in the subject's best interest that extra blood is taken for additional safety tests.

An additional 48 h residence in the ward, and additional outpatient visits, will be permitted in the event of a technical failure, and/or if extra observations or samples of blood are needed for safety purposes.

In the case of any post-dose samples for PK analysis, the following will not be regarded as protocol deviations:

- Deviations of not more than 5 min on measurements scheduled up to and including 4 h after dosing;
- Deviations of not more than 15 min on measurements scheduled from after 4 h to 24 h after dosing;
- Deviations of not more than 1 h on measurements scheduled more than 24 h after dosing; and
- Deviations of not more than 3 h on measurements scheduled on Day 5 and Day 7.

For all other procedures (including pre-dose PK sample), the following will not be regarded as protocol deviations:

Table 3. Permitted allowed time windows for all other procedures

Time point (Day 0)	Deviation window in relation to the scheduled time point
Pre-dose	Within 75 min before dosing ¹ (Part 1b: all procedures to be completed before breakfast)
Up to and including 4 h after dosing	± 10 min
After 4 h to 24 h after dosing	± 15 min
More than 24 h after dosing	± 1 hour
Ambulatory visits	Any time on the scheduled day

1. Urine collection for laboratory safety tests will be within 2 h of the scheduled time point and Day 0 urine sample to be collected pre-dose.

8.9. PK assessments

Blood samples for assay of emodepside will be collected at the time points indicated in the Schedule of assessments (Section 5). The exact date and time of PK blood sampling will be recorded in the CRF.

Blood samples for emodepside assay will be taken from either arm. Samples will be collected either via a cannula or by venepuncture. After processing, samples will be frozen and transported on dry ice to the Bioanalysis Laboratory. Detailed instructions for collection, processing, storage, and transport of samples will be provided in the Study Procedures Manual. Blood volumes for PK samples are shown in Table 4.

Plasma will be analyzed for emodepside using a validated assay method. Full details of the method will be presented in a separate document and all the results will be reported in the bioanalytical report at the end of the study. On the Profile Day (Day 0), frequent blood samples will be collected for PK estimation and emodepside plasma concentrations. The following PK parameters of emodepside will be derived for each subject:

Pharmacokinetic parameters

Text Symbol	Definition	Calculation
Concentrations and times		
C_{\max}	Maximum (peak) plasma concentration	The maximum (peak) plasma concentration will be obtained directly from the concentration-time data.
C_{\max}/Dose	Dose-normalised C_{\max}	The dose-normalised C_{\max} will be calculated as C_{\max} / Dose administered
$C_{\max,\text{norm}}$	Observed maximum plasma concentration corrected by dose and body weight	The C_{\max} normalised by dose and body weight will be calculated as $C_{\max} / (\text{Dose administered} * \text{body weight})$

Text Symbol	Definition	Calculation
t_{\max}	Time to reach maximum (peak) plasma concentration	The first time of maximum (peak) plasma concentration will be obtained directly from the concentration–time data.
Half-life		
λ_z	Terminal rate constant	The apparent terminal phase rate-constant (λ_z) will be estimated by linear regression of logarithmically transformed concentration versus time data.
$t_{1/2,0-24h}$	Dominant half-life	The half-life calculated from the terminal slope of the log concentration-time curve (0–24 h), as follows: $t_{1/2} = \frac{\log_e 2}{\lambda_z}$
$t_{1/2}$	Terminal elimination half-life	The terminal half-life calculated from the terminal slope of the log concentration-time curve, as follows: $t_{1/2} = \frac{\log_e 2}{\lambda_z}$
Points terminal	Number of points for λ_z	The number of time points used in calculating λ_z
Areas under the curve		
AUC_{last}	Area under the plasma concentration-time curve from time zero to time of last measurable concentration	The area under the concentration-time curve from zero time (pre-dose) to the time of last quantifiable concentration will be calculated using the (specified) trapezoidal method.
AUC_{0-7d}	Area under the plasma concentration-time curve from time zero to 7 days	The area under the concentration-time curve from zero time (pre-dose) to 7 days will be calculated using the (specified) trapezoidal method. If λ_z is not estimable, a partial AUC is not calculated (when $t_{\text{last}} < t$).
AUC_{0-7d}/Dose	Dose-normalised AUC from time zero to 7 days	The dose-normalised AUC from time zero to 7 days will be calculated as $AUC_{0-7d}/\text{Dose administered}$
$AUC_{0-7d,\text{norm}}$	Area under the concentration-time curve from time zero to 7 days corrected by dose and body weight	The AUC from time zero to 7 days normalised by dose and body weight will be calculated as $AUC_{0-7d}/(\text{Dose administered} * \text{body weight})$
Mean residence time		
MRT_{last}	Mean Residence Time	The mean residence time will be

Text Symbol	Definition	Calculation
		calculated using: $MRT = \frac{AUMC}{AUC_{last}}$

8.10. Total blood volume

The blood volume planned to be collected from each subject during the course of this study is detailed in Table 4. Additional samples may be required in the event of AEs. The planned total blood volume to be taken from each subject during the study is 158 mL.

Additional blood may need to be collected for assay of emodepside, or for laboratory safety tests. No more than an extra 80 mL blood will be taken.

Table 4. Blood volumes

Test	Planned number of tests	Volume (mL)	Total planned blood volume (mL)
Haematology	7	2	14
Biochemistry	7	2.5	17.5
Coagulation	7	3	21
Serology	1	2.5	2.5
Emodepside PK	18	5	90
Discard (when using a cannula)	13	1	13
		Total	158 mL

When using a cannula: after each blood sample, the cannula will be flushed with 3 to 5 mL normal saline, to keep it patent. In order to minimise dilution of each subsequent blood sample with normal saline, the following procedure will be used: about 1 mL will be drawn via the cannula into the sampling syringe, and discarded. The definitive blood sample will then be taken.

8.11. Assessment of Safety

Safety of the treatments will be assessed through routine monitoring of adverse events.

From screening (for AE onset after the subject signs the ICF), daily during the in-patient phase, then at the outpatient and Follow-Up Visits, the patients will be enquired about current adverse events or any events observed during the period previous to the visit.

In addition, 12-lead ECG recording, regular measurement of vital signs and physical examinations, clinical laboratory parameters monitoring, will be made at scheduled follow-up visits. (See Section 9 for AE recording and reporting, and the descriptions

below.)

8.11.1. 12-lead ECG Safety recording

Standard 12-lead ECGs will be recorded at the times given in the Schedule of assessments (Section 5). Triplicate ECGs will be done at screening (about 1 minute between recordings); single readings will be done at all other time points. Instructions for recording and handling of the ECGs will be included in the Study Procedures Manual. Any ECG abnormality confirmed by repeat will be assessed for clinical significance and if so reported as an adverse event (see AE definition in Section 9.1). If out of range at screening, the ECG may be repeated once.

8.11.2. Vital signs

BP and HR will be measured, in the supine position after 10 minutes rest, at times detailed in the Schedule of assessments (Section 5).

BP and HR will be measured using using SpaceLabs oscillometric equipment.

During the trial, vital signs will be repeated if they fall outside the following ranges:

- Supine systolic BP: 85 – 160 mm Hg
- Supine diastolic BP: 40 – 90 mm Hg
- Supine HR: 35 – 100 beats/min

If the result of the repeat measurement is still out of range, the Investigator will make an assessment of clinical significance (if the abnormality is assessed as clinically significant, it will be reported as an adverse event) and decide on an appropriate course of action. If out of range at screening, vital signs may be repeated once.

Oral temperature will be measured using oral thermometers.

8.11.3. Physical examination and neurological examination

Physical examination: will be done by a physician. The following will be examined: general appearance; head, ears, eyes, nose and throat; thyroid; lymph nodes; back and neck; heart; chest; lungs; abdomen; skin; and extremities; and the following systems will be assessed: musculoskeletal and neurological.

At certain time points, as detailed in the Schedule of assessments (Section 5), a brief (symptom-directed) physical and short neurological examination will be performed.

Height and body weight will also be measured at screening; body weight will be measured on Day –1.

Neurological examination will be done by a physician, in case it is clinically indicated, or to investigate treatment-emergent AEs. At the time-points in the Schedule of assessments (Section 5), a short neurological examination will be done, which includes an informal psychological assessment (e.g. orientation to place and time). Any abnormalities will trigger the full neurological examination or opening of an AE as appropriate. The full neurological examination may include (but is not limited to) any of the following: alertness, speech, language, and comprehension; cranial nerves; motor exam; coordination/cerebellar function; tremor of the hands, legs and head (postural, kinetic and rest tremor); sensation; gait and postural stability (Pull test);

mood; and sleepiness. Abnormalities assessed as clinically significant will be reported as adverse event (see AE definition in Section 9.1).

8.11.4. Clinical Laboratory Safety Assessments

Processing of samples will be done by the HMR Analytical Laboratory in accordance with the laboratory's standard operating procedures, and additional information may be found in the Study Reference Manual.

The HMR Analytical Laboratory will do safety tests on blood and urine samples using instruments interfaced to a validated laboratory information management system (LIMS). Data from analysers that are not interfaced will be entered manually into the LIMS. Confirmed abnormal laboratory results (after repeat) will be assessed for clinical significance and reported as AEs if necessary.

Collection of samples for laboratory safety tests: Blood will be taken for haematology (2 mL in EDTA), and biochemistry (2.5 mL in tubes with a gelatin plug), and coagulation (3 mL in sodium citrate). At screening, blood will be taken for serology (2.5 mL in tubes with a gelatin plug). Blood samples will be collected into 13 x 75 mm tubes. Urine will be collected in Universal containers. Samples will then be transferred to the laboratory.

Laboratory abnormalities considered AEs:

Laboratory abnormalities assessed as "clinically significant" have to be reported as an AE only if they meet AT LEAST ONE of the following conditions:

- The abnormality suggests a disease and/or organ toxicity AND this abnormality was not present at the screening visit or is assessed as having evolved since the screening visit
- The abnormality results in discontinuation of the study drug
- The abnormality requires medical intervention or concomitant therapy

When reporting an abnormal lab, a clinical diagnosis should be recorded rather than the abnormal value itself, if available (for example, "anaemia" rather than "decreased red blood cell count").

9. Adverse Event definitions and reporting

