7.6. Trial stopping criteria

The trial will be stopped if either of the following occurs:

- one or more serious AE that is considered to be related to emodepside; or
- 2 or more subjects with a severe or clinically significant AEs, considered to be related to emodepside, that occurs in the same treatment group

If, after an internal safety review, it is appropriate to restart the trial, a substantial amendment will be submitted to the Medicines and Healthcare products Regulatory Agency (MHRA) and REC. The trial will not restart until the amendment has been approved by the MHRA and REC.

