9.1 Adverse Event definition

An *adverse event* will be defined as:

Any untoward medical occurrence in a clinical trial subject administered a medicinal product that does not necessarily have a causal relationship with that treatment. An AE can therefore be any unfavourable and unintended sign (e.g. an abnormal laboratory finding), symptom, or disease temporally associated with the use of a medicinal product, whether or not considered related to the medicinal product.

Furthermore the definition of an AE includes worsening (in severity and frequency) of pre-existing conditions ("Medical history") before first Investigational Medicinal Product (IMP) administration and abnormalities of procedures (i.e., ECG, X-ray, etc.) or laboratory results which are assessed as "clinically significant". Information on AEs must be evaluated by a physician. Each AE is to be classified by the

Investigator as serious or non-serious. This classification will determine the reporting procedure for the event.

What is not an AE?

- Medical conditions present at the initial study visit that do not worsen in severity or frequency during the study are NOT considered as AEs.

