12.2 Derived and Transformed Data

Baseline will be considered to be the latest value obtained before study drug administration (e.g. Day 0, pre-dose; or Day -1 if not recorded pre-dose; or Screening if not recorded elsewhere (e.g. body weight)).

Laboratory data will be reported in standard units. Out-of-range laboratory tests may be repeated. If a test is out-of-range at a baseline time point and repeated before dosing, the latest repeat value before dosing will be used as baseline. However, if a test is out-of-range and repeated at any other time during the study, the out-of-range value (not the repeat value) will be included in statistical summaries.

TriPLICATE ECG and vital sign measurements will be made at pre-dose on Day 0 and the mean of the three measurements for each subject will be used as their baseline value for that session.

The pharmacokinetic parameters to be derived are given in Appendix B.

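### Protocol 8.11.4 and 9.1 conflict on when a clinically significant laboratory abnormality is an AE, and 8.11.4 judges change against screening rather than the pre-dose baseline

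*Protocol*

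**What the plan says.** Protocol 9.1 extends the AE definition to abnormalities of procedures "or laboratory results which are assessed as" clinically significant, and adds no further test. It then excludes medical conditions that were present at the initial visit and have not worsened.

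Protocol 8.11.4 says that clinically significant laboratory abnormalities "have to be reported as an AE only if they meet AT LEAST ONE of the following conditions". The first condition has two parts: the result must point to disease or toxicity in an organ, with the added requirement that "this abnormality was not present at the screening visit or is assessed as having evolved since the screening visit". The second is that the abnormality leads to discontinuation of study drug. The third is that it needs medical intervention or concomitant therapy.

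The parallel sections on ECG (8.11.1), vital signs (8.11.2) and neurological findings (8.11.3) have no such list. There, a finding assessed as clinically significant is reported as an AE.

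Screening may be up to 28 days before dosing (Protocol 8.3). SAP 12.2 takes the latest value before dosing as baseline, and SAP 12.4 uses Day 0 pre-dose for the laboratory change flags. Protocol 11.6.5 and SAP 14.2 also define treatment emergence by comparison with the state before dosing.

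**The concern.** Two sections of one protocol give site staff different answers to the same question, and neither is said to take precedence. Laboratory results are also the only safety measure with this extra filter.

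The answer has consequences. AE status decides whether a result appears in the TEAE and drug-related TEAE tables by formulation. It also decides whether the result can count towards the stopping condition in Protocol 7.6, which refers to "2 or more subjects with a severe or clinically significant AEs, considered to be related to emodepside" in the same treatment group.

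The comparator raises a second question. A rule meant to pick up what happened after dosing should start from the subject's state just before dosing. Under 8.11.4 it starts from a sample that may be four weeks old.

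**Working it through.** There is no planned figure to reproduce, so the check sets the two rules side by side.

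**Conflict between the rules.** Take a laboratory abnormality already assessed as clinically significant, and classify it three ways: suggests disease or organ toxicity (yes/no), status against screening (new, present and evolved, present and unchanged), needs intervention or therapy (yes/no). Discontinuation is left out because each subject receives one dose. That gives 2 × 3 × 2 = 12 combinations. Rule 8.11.4 is (toxicity and not unchanged) or treated. Rule 9.1 is taken with and without its exclusion, because it speaks of medical conditions and an isolated laboratory value may or may not be one.

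| Combination | Cells | 8.11.4 | 9.1 with exclusion | 9.1 without |
|---|---|---|---|---|
| New or evolved, suggests toxicity, treated or not | 4 | AE | AE | AE |
| New or evolved, no toxicity, treated | 2 | AE | AE | AE |
| New or evolved, no toxicity, untreated | 2 | not AE | AE | AE |
| Unchanged, treated, toxicity or not | 2 | AE | not AE | AE |
| Unchanged, untreated, toxicity or not | 2 | not AE | not AE | AE |

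With the exclusion, the sections disagree in 2 + 2 = 4 of 12 cells, two with 8.11.4 narrower and two with it broader. Without the exclusion they also disagree in 2 + 2 = 4 of 12, all with 8.11.4 narrower. The third row conflicts under both readings. These are counts of logical cases and say nothing about how often each occurs.

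**Comparator.** Suppose, as an illustration, ALT of 70 IU/L at screening, 35 pre-dose and 70 on Day 3.
- Change from the SAP baseline: 70 − 35 = +35, above the Appendix A limit of +30.
- Change from screening: 70 − 70 = 0.

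Appendix A gives no reference limits. If the upper limit is at least 35 and below 70, the pre-dose value is normal and the Day 3 value is double-flagged under SAP 12.4. Under 8.11.4 the abnormality was present at screening, so unless it needs treatment its reporting turns on whether a return to the same value counts as having evolved. The protocol does not say. The double flag is not itself an assessment of clinical significance; the case matters only if the Investigator makes that assessment.

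**Effect on 7.6.** Two subjects in an arm of 12 (2/12 = 16.7%) are enough. Two related results from the third row of the table, in one arm, could count if staff follow 9.1 and would leave no AE to count if they follow 8.11.4.

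**The case against.** The best defence is that 8.11.4 merely applies 9.1 to laboratory data, and that the disputed class is nearly empty: a result both clinically significant and related to emodepside will seldom fail to suggest disease or organ toxicity. The SAP also lists double-flagged values and summarises their frequencies whatever their AE status (14.5), and the Safety Review Group sees all safety data. This limits the size of the problem. It does not remove the contradiction, and the listings do not feed the 7.6 count. They also have gaps: SAP 17.1 plans no listing of potentially important coagulation values, and magnesium has no change limit in Appendix A, so it cannot be double-flagged. The complete data listings would still show these values.

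On the comparator, the defence can say that 9.1 too refers back to the initial visit, and that 70–35–70 can be assessed as evolved. Both are fair. They make the outcome uncertain rather than settled.

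Some stronger readings are tempting but unsupported:

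- *That 8.11.4 removes transient abnormalities.* None of its conditions concerns duration, and a short-lived new result suggesting toxicity is an AE under both sections. The section does say "Confirmed abnormal laboratory results (after repeat) will be assessed for clinical significance and reported as AEs if necessary", but confirmation on repeat is also the convention for ECG and vital signs and does not conflict with 9.1, which likewise needs a clinical-significance assessment. The glucose rises in the first-in-human study were not AEs because they were not judged clinically significant (Protocol 1.4).
- *That it removes everything seen at screening.* It keeps what has evolved or needs treatment.
- *That the discontinuation condition is harmful.* In a list where one condition suffices, a condition that cannot be met excludes nothing.
- *That SAP 12.2 contradicts the repeat rule.* Its statement that "the out-of-range value (not the repeat value) will be included in statistical summaries" governs summaries, not AE status.

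**Conclusion.** The conflict is real but narrow. Under either reading of 9.1, a clinically significant laboratory result that is new or worsened, suggests no disease or organ toxicity and needs no treatment is an AE in 9.1 and not reportable in 8.11.4. Separately, the screening comparator leaves open whether an abnormality seen at screening, normal pre-dose and abnormal again after dosing is an AE.

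The documents give no frequency for either class, so the number affected cannot be computed; it is probably small. The point still deserves correction before analysis, because AE status feeds the TEAE tables and the 7.6 count and the remedy is cheap. The conclusion assumes that no other controlling document, such as the Study Procedures Manual, sets the order of precedence; the protocol and SAP do not.

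**What to change.** Reconcile 8.11.4 and 9.1 into one reporting rule. The simplest form has 8.11.4 refer to 9.1, as the ECG and neurological sections do, so that a clinically significant laboratory result that is new or worsened is an AE. In both sections, judge post-dose results as new or worsened against the pre-dose baseline that SAP 12.2 and 12.4 already use, and say whether the 9.1 exclusion of unchanged conditions covers an isolated laboratory value. Then check that 7.6 reads as intended against that single definition. The confirmation step on repeat can stay. Deleting the discontinuation condition is optional tidying.

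This changes protocol wording only and needs no extra samples. The downside is a few more AE records.
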